The purpose of the proposed project is to provide athletes and the scientific community with data pertaining to the acute influence of edible marijuana on exercise performance, and the physiological responses to standardized exercise. Specifically, we wish to determine: 1. The influence of edible marijuana on cardio-respiratory and metabolic responses to standardized cycle ergometer exercise. 2. The influence of edible marijuana on endurance exercise (time-trial) performance.

What do the investigators hope to learn from the project?

We wish to determine if edible marijuana, ingested prior to exercise, is ergogenic (improves performance) or ergolytic (decreases performance). We hypothesize that edible marijuana will be ergolytic.

Describe how sharing results of this study could influence behavior, practice, theory, future research designs. Specifically, how will study results apply to a larger population than the studied participants?

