List all research activity procedures in which a participant will be involved, including follow-up procedures. Please provide details.

Procedure Description

Establishing Relevant Physiological Characteristics of Study Participants and Habituation to Exercise Protocols. Session 1 - Overview Participants will answer questions pertaining to health, medical history and habitual use of marijuana. They will be assessed for body composition, maximal oxygen uptake and electrocardiographic responses to exercise. Session 2 - Overview The purpose of this session is to habituate the participants to the exercise testing protocol. Habituation/familiarization with protocols decreases within participant variability. Participants will perform standardized stationary cycle ergometer exercise, and then complete a performance test (time-trial). Session 3 - Overview This session will be identical to session 2. Session 1 - Detailed description. This visit is a one time visit with duration of ~ 90 minutes. During this visit participants will complete the Informed Consent, provide a brief medical history, answer questions pertaining to habitual use of marijuana, and will undergo basic measures of body composition (height, weight, and waist and hip circumference, and DEXA), and maximal oxygen uptake (VO₂max). An exercise stress test, with 12-lead ECG and blood pressure measurement will also be completed. The medical history questionnaire will help identify contra-indications to study participation. Questions pertaining to habitual marijuana use will confirm that participants meet the inclusion criteria and may also serve as a co-variable: it is possible that the interaction between marijuana and exercise performance may be influenced by degree of habitual consumption. Previously we have demonstrated that body composition is a known physiological determinant of the resultant circulating concentrations of cannabis-derived products following ingestion. While not a primary outcome, DEXA data will be used as an important statistical co-variable in our final analysis. The graded exercise stress test with 12-lead ECG and blood pressure measurement will be used to identify potential contraindications to study participation. The guidelines provided by the American College of Sports Medicine pertaining to physician supervision will be followed. During the graded exercise test, exhaled gases will be collected in order to calculate maximal oxygen uptake (VO₂max). The VO₂max measurement will characterize the endurance capacity of the participants; this is a standard and indeed expected measurement for all human studies of endurance exercise physiology. Session 2 - Detailed description The purpose of this session is to habituate the participants to

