
the exercise testing protocol. Habituation/familiarization with protocols decreases within-participant variability (i.e. the day-to-day differences between test results). Participants will perform standardized stationary cycle ergometer exercise, and then complete a performance test (time-trial). Standardized stationary cycle ergometer exercise will comprise 24-minutes of cycling: 8 minutes at 50 Watts, 8 minutes at 100 Watts, and 8 minutes at 150 Watts. During this cycling heart rate and blood pressure will be measured and recorded. Exhaled gases will be collected in order to calculate oxygen uptake (VO₂), carbon dioxide production (VCO₂) and ventilation (VE). The rationale for the chosen work rates is they represent low-to-moderate intensity exercise, and they will provide three observations that will be used to determine the relationship between work rate and cardio/respiratory/metabolic responses to standardized exercise. This information will provide insight as to the physiological responses to controlled exercise and may explain and differences we may detect in uncontrolled, exertion driven exercise (i.e. the time-trial). The rationale for the duration of each stage (8 minutes) is this duration is adequate for the participants to attain steady-state physiology. Participants will then be asked to cycle a distance equivalent to 10-km (~6 miles) as quickly as possible, on the stationary ergometer (i.e. a laboratory based time-trial). Previous studies have demonstrated that practice visits helps to improve time-trial performance in subsequent tests. This type of exercise test is a standard protocol in our lab (See Protocols 09-1363H, 10-2065H, 15-5979H, 11-2626H, 11-3032H, 13-4366H, 16-6570H, 17-7252H, etc.). Following completion of the time-trial, participants will complete one 30-second bout of high intensity cycle ergometer exercise (also known as a Wingate Test) during which we will measure peak power output. This type of exercise is a standard procedure in our lab (See Protocols 09-1124H, 09-1363H, 10-2065H, and 15-5979H) and has been safely performed in young and older, previously sedentary and endurance trained adults. Session 3 - This session will be identical to session 2.

This procedure is:

Research Activity Involving Participants, Participants Data, or Biospecimens

This procedure is:

Standard of Care or Established Practice

Where and when will this procedure take place?

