These procedures will be completed during the first three study visits. These procedures will take place in the Human Performance Clinical Research Lab, in the Department of Health and Exercise Science, on the main CSU Campus.

Who will conduct this procedure?**Personnel**

[name]

Personnel

[name]

Personnel

[name]

Personnel

[name]

Personnel

[name]

Indicate the frequency and duration of visits/sessions as well as the subject's total time commitment for the study.

3 Sessions: Session 1 ~ 90 minutes. Session 2 ~ 60 minutes. Session 3 ~ 60 minutes Total time commitment for the first 3 sessions = $90+60+60 = 210$ minutes (3 hours 30 minutes)

Describe how the data will be collected (i.e. in person or online).

Questionnaires may be completed in advance of Session 1 online (via email) or in-person. All other activities will be completed in person.

Will any video, photography, or audio be recorded as part of this procedure?

No

Will data be collected anonymously?

No

Procedure Description

Physiological Responses to Standardized Exercise and Time-Trial Performance - placebo vs. edible marijuana. Sessions 4 and 5 will comprise two almost identical sessions that will be very similar to Sessions 2 and 3. Primary differences will be: (1) the venue for the sessions: these will be field-based locations. Based on our previous protocol (Protocol # 1909) these locations will typically be residential locations chosen by the research participants. (2) these visits will involve ingestion of either a placebo (something that has no physiological effect) or edible marijuana. (3) Additional procedures will include blood collection (detailed below), and pre-session preparation (marijuana abstention, etc. - detailed below). The need for a field-based, off-campus location is dictated by CSU rules banning the possession of marijuana on campus. Consistent with our previously approved protocol, the venue will be chosen by the participant (e.g. a residential location occupied by the participant and/or friends/relatives of the participant). To remain in compliance with state law and CSU rules, we will follow the same procedures described in our previous protocol.

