## Statistical Analysis Plan

All data, unless otherwise stated, are expressed as mean and standard deviation. To compare baseline values between placebo and edible marijuana for circulating concentrations of THC, and THC metabolites, one-way analysis of variance (placebo vs edible marijuana) was used, unless a non-parametric equivalent (i.e. one way analysis of variance on ranks) was required on account of unequal variance. The standardized exercise statistical analysis was conducted in R (R Core Team; Vienna, Austria) as linear mixed models using the Lmer and LmerTest packages (Bates et al., 2015), and Emmeans package was used for post hoc Tukey testing to explore main effects and interactions. Time and Condition were considered fixed effects, whereas Subject was considered a random effect to account for the repeated measures. Unlike an electrically braked ergometer, it is not feasible to externally fix the work rate on an air braked ergometer; the actual work rate is determined by the damper setting and the participant's pedal cadence. During the standardized exercise test, participants were instructed to exercise at 50, 100 and 150 W. Accordingly, for statistical analysis of these data, work rate error, defined as the difference between the prescribed work rate and the actual work rate, was considered as a covariate in our model. One- and two-way analysis of variance, with repeated measures, were employed to detect differences among variables during the performance of the FTP20 and in the sprint to fatigue tests using SigmaPlot 14.5 (Systat Software Inc., San Jose, California). Specifically, one-way repeated measures ANOVA was used to compare mean work rate (placebo vs edible marijuana). Two-way ANOVA with repeated measures (time) was used to compare power outputs across consecutive stages (placebo vs edible marijuana). One-way repeated measures ANOVA was used to compare mean power, peak power, time to fatigue, and total work done (placebo vs edible marijuana) during the sprint to fatigue tests. Significance was defined as  $p < 0.05$ . Wherever a significant difference was detected, a post-hoc Tukey test was utilized to further explore these differences.

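### The SAP analyses an FTP20 and a sprint to fatigue, whereas the protocol's procedures specify a 10-km time trial and a 30-second Wingate; the performance endpoints must be reconciled

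*SAP*

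**What the plan says.** The protocol's Summary and Purpose gives the second aim as "The influence of edible marijuana on endurance exercise (time-trial) performance". In the Procedures section, the detailed description of Session 2 defines the endurance test: "Participants will then be asked to cycle a distance equivalent to 10-km (~6 miles) as quickly as possible, on the stationary ergometer". The sprint follows: "participants will complete one 30-second bout of high intensity cycle ergometer exercise (also known as a Wingate Test". Peak power is the only outcome named for it. Session 3 repeats Session 2. Sessions 4 and 5, the treatment sessions, come under the title "Physiological Responses to Standardized Exercise and Time-Trial Performance - placebo vs. edible marijuana" and refer back to the same time trial and the same 30-second sprint, with blood sampling added. The physical-risk text under Risks and Benefits also names the time trial and the Wingate.

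The SAP mentions neither. It applies one- and two-way repeated-measures ANOVA "to detect differences among variables during the performance of the FTP20 and in the sprint to fatigue tests". From the context, the FTP20 outcomes are mean work rate and power over consecutive stages. For the sprint, "One-way repeated measures ANOVA was used to compare mean power, peak power, time to fatigue, and total work done".

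The abstract in the Close Request's Summary of Findings, at the front of the protocol file, agrees with the SAP: it reports a 20-minute FTP20 and a sprint to volitional fatigue. The procedures in that same file do not mention the FTP20.

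**The concern.** A reader who takes the protocol and SAP together finds a planned endurance test with no analysis, and an analysed endurance test with no description in the procedures. The same holds for the sprint.

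Two things are at stake. First, the abstract concludes that 10 mg of THC neither improved nor impaired performance. That conclusion rests on tests the procedures do not contain, so its standing depends on whether those tests and outcomes were fixed before the data were seen. Second, the protocol justifies Sessions 2 and 3 as practice that reduces within-participant variability, and the tests it has participants practise are the 10-km trial and the Wingate. The documents do not show whether participants were habituated to the tests that were analysed.

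**Working it through.** No sample-size, power or significance figure is involved, so the check is a comparison of the two texts. The left column comes from the protocol's Procedures section. The right column comes from the SAP, with the end rules taken from the close-out abstract.

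| Feature | Procedures | SAP and abstract |
|---|---|---|
| Endurance test | 10-km time trial | FTP20 |
| Ends when | 10 km is covered | 20 minutes have passed |
| Outcome | Not named; completion time is the natural one | Mean work rate; power by stage |
| Sprint test | Wingate | Sprint to fatigue |
| Ends when | 30 seconds have passed | Volitional fatigue |
| Outcome | Peak power | Mean power, peak power, time to fatigue, total work |

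1. **Overlap of tests.** The procedures contain two performance tests and the SAP analyses two. They have none in common: 0 of 2 in either direction.

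2. **Could these be two names for the same test?** No. The 10-km trial fixes distance and leaves time free. The FTP20 fixes time and is scored as power. The Wingate fixes time at 30 seconds, whereas the sprint to fatigue leaves time free.

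3. **Overlap of outcomes.** Peak power is the only performance outcome named in both documents, that is, 1 of the SAP's 4 sprint outcomes. It comes from sprints with different end rules.

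4. **Time to fatigue.** If every participant completes a 30-second bout, each person's difference between conditions is 30 − 30 = 0 seconds, which leaves nothing to compare. This outcome therefore has no counterpart in the planned sprint and makes sense only for an open-ended one.

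5. **Extent.** The standardised exercise at 50, 100 and 150 W appears in both documents. The mismatch is confined to the performance tests, and the first aim is not affected by it.

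**The case against.** The strongest reply is that the SAP is written in the past tense and agrees with the abstract, so it probably describes the tests that were actually performed, and nothing in it is shown to be a wrong analysis of those tests. That stands. The fault is an unreconciled change of endpoint, not a faulty ANOVA. There is continuity as well: both documents have a hard endurance ride followed by a maximal sprint, the second aim itself states no distance, and an FTP20 can address the general question of whether the product helps or harms performance. This also stands, but it does not give the specified time trial an analysis.

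Several stronger readings are tempting, and the documents do not support them.

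- *The tests were switched after the data were seen.* Parts of both documents are missing from the available text and may hold an amendment, a date or a reason. The reported performance results are also null (p > 0.45 for FTP20, p = 0.864 for sprint peak power) and do not support the investigators' ergolytic hypothesis. That is no sign of a switch made to obtain the expected effect, although it does not exclude selective reporting.
- *The FTP20 and the open-ended sprint replaced the planned tests.* The documents do not say whether the 10-km trial and the Wingate were dropped, or were run and not reported.
- *Some of the SAP's four sprint outcomes are redundant.* In a completed 30-second bout, total work would be 30 seconds times mean power. The SAP does not claim to analyse such a bout, and in a sprint to fatigue that relation does not hold.
- *The close-out form's statement that the study was completed as planned proves a misreport.* It is an administrative field that does not say which version of the plan it refers to, so it adds little.

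**Conclusion.** The mismatch holds and needs to be put right before the performance conclusion is relied on. Both performance tests differ between the documents, the time trial named in the second aim has no analysis as written, and one SAP sprint outcome cannot arise from the planned sprint.

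The conclusion rests on the procedures text and the SAP as they stand. It assumes that the abstract's end rules (20 minutes; volitional fatigue) are those of the tests the SAP names. It does not assume when or why the tests changed: the timing is unknown. How firmly one can say that the product neither improved nor impaired performance therefore depends on records not seen here. An amendment, if there is one, could settle the timing, but the procedures and the SAP would still describe different tests until they are reconciled.

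**What to change.** Add a dated statement to the SAP and the report that says:

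- which performance tests were run in each of Sessions 2 to 5;
- whether the 10-km trial and the 30-second Wingate were dropped, or were run and not reported;
- when the tests changed relative to the first Session 4, and why.

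Then:

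- If 10-km or Wingate data exist, analyse and report them with the same repeated-measures comparison of placebo and edible marijuana.
- If records show that the FTP20 and sprint-to-fatigue outcomes were specified before the data were seen, cite those records.
- If not, label those outcomes as changed from the protocol and exploratory, word the conclusion on performance to match, and do not choose a primary outcome now.

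The cost is a short statement and outcome labels, plus a small added analysis if the planned tests were run. The downside is that the performance conclusion may have to be reported as exploratory.
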